De-identified study samples will be stored in -80°C freezer at USARIEM in room 322 or 304 for potential future use and maintained indefinitely. Only personnel assigned to the research study by the principal investigator will have access to samples. The de-identified data and samples will remain under the control of the PI and may be shared with outside collaborators for future research. Any use of the samples outside of this defined protocol will be submitted as a protocol amendment or a new protocol.

B5.7 Devices, Drugs, Dietary Supplements, Nutritional Supplements, And Biologics

B5.7.1 Devices

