Lead Site: N/A

Performance Site: N/A

SECTION B: RESEARCH METHODOLOGY

B1. ABSTRACT

[figure not shown]
Two recent investigations from our laboratory have consistently observed a reduction (30-50%) in the rate of exogenous glucose oxidation in native lowlanders performing metabolically-matched, steady-state exercise at high altitude (HA) compared to sea level (SL). Accompanying lower rates of exogenous glucose oxidation at HA were increases in circulating glucose and insulin concentrations, and reduced glucose rate of disappearance and metabolic clearance rate. Apparent hypoxia-induced insulin insensitivity along with alterations in glucose kinetics suggests reduction in glucose uptake by the peripheral tissue is a primary factor contributing to reductions in exogenous glucose oxidation at HA. As such, the primary objective of this study is to determine the ability of an insulin sensitizer (Pioglitazone, PIO) to enhance exogenous glucose oxidation and metabolic clearance rate during metabolically-matched, steady-state exercise during acute HA exposure compared to placebo (PLA) in native lowlanders. Secondary objective of this study will be to assess the impact of PIO on markers of inflammation and iron status compared to PLA. This randomized crossover placebo control double blinded study will examine substrate oxidation and glucose kinetic responses to ingesting supplemental carbohydrate (glucose) during metabolically-matched, steady-state exercise with acute (~5 h)

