Rapid deployment to remote mountainous regions will occur during MDO. Unacclimatized Service members experience altered carbohydrate metabolism, causing an increased reliance on glycogen for fuel, concomitant with a blunted ability to take up and oxidize exogenous carbohydrate. These negative physiological effects likely exacerbate declines in physical performance at HA. This proposal directly supports the Military Operational Medicine Research Program's Physiological Health and Performance Program Area under the Biomedical Performance Enhancement (BPE) Work Unit. Specifically, the proposed work aligns to BPE Strategic Plan's *Technical Objective 1.1.3: Material solutions (pharmacological) that enhance Soldier resistance to environmental stressors*.

This proposal will provide guidance for use of PIO to enhance exogenous carbohydrate oxidation at HA operations, and will provide the opportunity to determine if carbohydrate supplementation can indeed enhance performance if substrate metabolic dysregulation is avoided during HA exposure. Information from this proposal would be valuable to operational partners such as USSOCOM and the 10th Mountain Division who engage in HA MDO.

B4. OBJECTIVES/SPECIFIC AIMS/RESEARCH QUESTIONS

Objective:

1. Determine the effects of PIO on exogenous glucose oxidation and glucose turnover during exercise under acute HA exposure compared to PLA.
2. Determine the effects of PIO on inflammation during acute HA exposure compared to PLA.
3. Determine the effects of PIO on markers of iron status during acute HA exposure compared to PLA.

Hypotheses:

1. Exogenous glucose oxidation, Rd, and MCR during metabolically-matched, steady-state exercise at HA will be greater after PIO administration compared to PLA.
2. Inflammation will be lower during acute HA exposure after PIO administration compared to PLA.
3. Markers of iron status will be altered during acute HA exposure after PIO administration compared to PLA.

B5. RESEARCH PLAN

B5.1 Research Design

This study will be a randomized crossover double blind placebo control trial.

Table 1: Study Timeline

Study Day	Baseline					Trial 1					Washout	Trial 2				
	SV	1	2	3	4	5	6	7	8	9		20	21	22	23	24
Medical Screening	X															
Body Composition		X														
Height		X														
Weight		X								X						X
VO ₂ peak		X	X													
High Altitude Exposure			X							X						X
Practice Exercise				X	X											
Glycogen Normalization						X							X			

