5.7.1.3 Any device not approved by the FDA

N/A

B5.7.2 Drugs

B5.7.2.1 FDA-approved and used in accordance with the approved labeling

B5.7.2.2 FDA-approved and used in a manner not in accordance with its approved labeling
Pioglitazone, Thiazolidinedione, Takeda Pharmaceutical Company

B5.7.2.3 Any drug not approved by the FDA

N/A

B8 Statistical Analysis

B5.8.1 Sample Size Estimation

Based on results of exogenous carbohydrate oxidation and MCR rate between SL and HA in our previous investigation (3, 4), a sample size of 8 is required to achieve 80% power (**Table 4**). We will request to enroll up to 24 individuals to account for withdrawals from the study.

Table 4: Previous study effect sizes

Study	Outcome	Delta	Effect Size	Sample Size
Young et al. (4)	Exogenous Glucose Oxidation	0.35 ± 0.21	1.11	7
Margolis et al. (3)	Exogenous Glucose Oxidation	0.09 ± 0.06	0.95	8
Margolis et al. (3)	MCR	3.1 ± 2.0	0.98	7

B5.8.2 Data analysis

Statistical analyses will be conducted using either SPSS (IBM Corp. Armonk, NY), SAS 9.3 (SAS Institute Inc., Carey, NC), or equivalent. Shapiro Wilks will be used to assess all data for normality. Data that are not normally distributed will be log transformed for statistical analysis. Paired T tests will be used to assess effects of study arms (HA+PIO vs. HA+PLA) on chamber conditions (barometric pressure, temperature, and humidity), oxygen saturation, heart rate, $\dot{V}O_2$, $\dot{V}CO_2$, respiratory exchange ratio, ventilation exchange, total glucose and fat oxidation, plasma glucose, muscle, and liver oxidation. Mixed Model repeated measures ANOVA will be used to assess the effects of condition, time, and their interactions for breath ^{13}C -enrichments, exogenous glucose oxidation, and blood analytes. Bonferroni adjustments for multiple comparisons will be performed if significant interactions are observed.

SECTION C: HUMAN RESEARCH PROTECTIONS

C1. RECRUITMENT AND CONSENT

C1.1 Identification and Selection of Subjects

Volunteers will be recruited from the federally and non-federally employed civilian population, the Natick Human Research Volunteer (HRV) Pool, NSSC active duty military personnel, and the active duty population located at other military organizations, to include, but not limited to coordination with the NSSC Soldier and Squad Optimization and Integration Team (SSO-IT).

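### Hypothesis 1 joins three outcomes with no primary outcome, no any-one or all-three rule, no stated alpha and no error control across them

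*Combined protocol and SAP*

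**What the plan says.** Three places state the main question.

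- B1 Abstract, primary objective: whether pioglitazone is able "to enhance exogenous glucose oxidation and metabolic clearance rate during metabolically-matched, steady-state exercise". That is two outcomes; Rd is not named.
- B4, objective 1: "Determine the effects of PIO on exogenous glucose oxidation and glucose turnover during exercise under acute HA exposure compared to PLA".
- B4, hypothesis 1: "Exogenous glucose oxidation, Rd, and MCR during metabolically-matched, steady-state exercise at HA will be greater after PIO administration compared to PLA". That is three outcomes, all expected to rise.

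B5.8.1 bases the sample size on sea-level versus altitude differences in exogenous oxidation and MCR in earlier work and concludes that "a sample size of 8 is required to achieve 80% power". Table 4 has two rows for exogenous glucose oxidation, one for MCR and none for Rd.

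B5.8.2 assigns exogenous glucose oxidation to a mixed-model repeated-measures ANOVA and a list of other variables to paired t tests. Rd and MCR are named under neither. The only multiplicity rule is: "Bonferroni adjustments for multiple comparisons will be performed if significant interactions are observed". No alpha level or sidedness appears anywhere.

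**The concern.** A reader of the results will ask whether hypothesis 1 was supported, and the plan does not say how to answer. If exogenous oxidation rises and Rd and MCR do not, or the reverse, the trial could be reported as positive (one of three) or negative (not all three), and the choice can be made after the data are seen.

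The Bonferroni rule does not help. It is triggered by a significant interaction, so it covers condition-by-time comparisons within one outcome's model, not the three outcomes together. The 80% power does not settle it either: it belongs to single outcomes, so it describes neither the chance of all three succeeding nor a family of tests with controlled error. B3 expects the results to guide use of the drug at altitude, so the rule for calling the main hypothesis supported matters.

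**Working it through.** **1. The plan's own sample size.** Inputs from Table 4: effect sizes 1.11, 0.95 and 0.98, with stated sample sizes 7, 8 and 7. Power of a paired t test on n pairs comes from the noncentral t distribution with n − 1 degrees of freedom and noncentrality d√n. Smallest n for 80% power:

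- one-sided 5%: 7, 9, 8;
- two-sided 5%: 9, 11, 11;
- two-sided 5%, normal approximation: 7, 9, 9.

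The one-sided t calculation comes within one of every stated value. At n = 8 it gives power of 88%, 78% and 80%; two-sided, the figures are 77%, 64% and 66%. So the overall figure of 8 is roughly reproduced, one outcome at a time, if the tests are one-sided at 5%, which the plan does not say. The ratio of the tabulated delta to its ± value (0.35/0.21 = 1.67, 0.09/0.06 = 1.50, 3.1/2.0 = 1.55) differs from the stated effect sizes; I use the stated ones.

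**2. Assumptions for the illustration.** n = 8 and the 80% target are from B5.8.1. Not in the documents: a 5% level per test, paired t tests for all three outcomes, 80% power for each outcome including Rd, and the correlations. The turnover calculations in B5.4 define MCR as Rd divided by mean glucose concentration, so those two are linked by construction. Exogenous oxidation comes from breath isotope enrichment and carbon dioxide output.

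**3. Independent outcomes, in closed form.**

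- At least one false positive in three 5% tests: 1 − 0.95³ = 14.3%.
- At least one false rise with two-sided 5% tests (2.5% in the upper tail): 1 − 0.975³ = 7.3%.
- All three succeed at 80% each: 0.8³ = 51.2%.

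**4. Correlated outcomes.** Simulation of 400,000 trials per setting, 8 correlated paired differences. A standardised effect of 1.156 gives 80% power per outcome two-sided.

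| Correlation | Any one, two-sided, either direction | Any one, two-sided, rise only | Any one, one-sided 5%, rise | All three rise, 80% each, two-sided |
|---|---|---|---|---|
| 0 | 14.3% | 7.4% | 14.3% | 51.2% |
| 0.3 | 13.8% | 6.9% | 13.2% | 55.8% |
| 0.6 | 12.3% | 6.2% | 11.5% | 61.8% |
| 0.9 | 8.9% | 4.5% | 8.2% | 71.1% |
| Rd–MCR 0.9, exogenous 0.3 with each | 11.8% | 5.9% | 11.2% | 61.8% |

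The benchmark for one outcome is 5% in the first and third result columns and 2.5% in the second. One-sided tests with 80% power each (effect 0.978) give nearly the same joint power, 51.3% to 71.4%.

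**5. Using Table 4's effect sizes instead of 80% each.** With 0.95 for exogenous oxidation, 0.98 for MCR and an assumed 0.98 for Rd, all-three power at n = 8 over common correlations 0 to 0.9 is 50–71% one-sided and 28–54% two-sided.

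**The case against.** The strongest reply is that the wording already decides the matter: hypothesis 1 joins the outcomes with a plain conjunction, so all three must rise. That is the natural reading, and under it there is no inflation of error. But it is a hypothesis and not a decision rule, and if it were the rule, the 80% in B5.8.1 would not be the power of hypothesis 1.

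A second reply is that this is an eight-person mechanistic crossover which, by C8.4, is not meant to support a new indication or labelling. That is fair and limits the seriousness. It does not remove the need to say what counts as success.

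Several stronger readings are tempting, and the documents do not support them.

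- A reader might infer that the trial has a fixed false-positive rate of some 12–14%, or joint power of 51–63%. Those figures need an unstated 5% level and moderate correlations; higher correlation moves both.
- A reader might take the two-sided 9–14% as the chance of wrongly claiming a rise. It also counts significant falls. The chance of a false rise is about half that unless the tests are one-sided.
- A reader might infer three conflicting outcome sets. The glucose turnover named in objective 1 can cover both Rd and MCR, so it is compatible with hypothesis 1. The clear mismatch is the missing Rd in the abstract.
- A reader might treat the paired t calculation as the planned analysis. B5.8.2 assigns exogenous oxidation to a mixed model and names no test for Rd or MCR, so the calculation is a stand-in.

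**Conclusion.** The point holds as a gap in the decision rule. The main hypothesis spans three outcomes without a ranking, a success rule, a stated alpha or error control across them, and the stated power covers only two of the outcomes, each alone.

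The size is conditional on the settings in step 2. Over correlations of 0 to 0.9, an any-one rule raises the false-positive chance above the single-test level throughout, by a factor of about 1.6 to 3 (8.2/5 = 1.6; 7.4/2.5 = 3.0). An all-three rule gives joint power below 80% throughout, even when each outcome, including Rd, is granted 80%. The direction is secure for these correlations; the exact percentages are not properties of the trial.

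**What to change.** In B4 and B5.8.2:

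1. Name exogenous glucose oxidation as the single primary outcome. It is listed first in the abstract, objective 1 and hypothesis 1, and fills two of the three Table 4 rows.
2. State alpha and sidedness. The power figure must be rechecked against that choice, since step 1 shows it depends on it.
3. Test MCR and Rd afterwards in a prespecified fixed order, each only if the one before is significant. MCR then Rd is one acceptable order, not the only one. If the sponsor prefers not to rank the outcomes, use Holm across the three.
4. Name the test for Rd and MCR.
5. Make the abstract, objective 1 and hypothesis 1 list the same outcomes.
6. State in B5.8.1 that the 80% power applies to the primary outcome only.

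This is wording only: no added volunteers, samples or visits. The downside of the fixed order is that MCR and Rd become descriptive if exogenous glucose oxidation is not significant. Holm avoids that but costs power: its first step uses 0.05/3 = 0.0167 if the overall level is 5%, and at that level two-sided power at n = 8 is 54%, 40% and 43% for effect sizes 1.11, 0.95 and 0.98, against 77%, 64% and 66% at 5%.

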This randomized crossover placebo controlled double blinded study will examine substrate oxidation and glucose kinetic responses to ingesting supplemental carbohydrate (glucose) during metabolically-matched, steady-state exercise with acute (~5 h) exposure to HA (460 mmHg) after short-term (5 days) use of Pioglitazone (HA+PIO), or matched placebo (HA+PLA). Eight healthy, recreationally active males between the ages of 18-39 yrs will be enrolled. Following a muscle glycogen normalization period, volunteers will complete 80-min of metabolically-matched, steady-state (same absolute workload corresponding to $\sim 55 \pm 5\%$ of $\dot{V}O_{2\text{peak}}$ at HA) exercise on a treadmill, and consume 145 g of glucose (1.8 g/min) with HA+PIO and HA+PLA. A dual glucose tracer (^{13}C -glucose oral ingestion and $[6,6-^2\text{H}_2]$ -glucose primed, continuous infusion) technique and indirect calorimetry will be used to analyze endogenous and exogenous glucose oxidation, as well as glucose rate of appearance (Ra), disappearance (Rd), and MCR. Serial blood samples will be collected during each trial to assess endocrine and circulating substrate responses to exercise, carbohydrate, and hypoxia, with or without PIO. Isotope methodology and aerobic exercise protocols will be identical to our previous work (3, 4), allowing comparison of outcomes across studies. All

trials will be conducted in the USARIEM hypobaric/hypoxic chamber and be separated by a minimum 10-d washout period.

A member of the research team will generate a randomization scheme using a random number generator (<http://randomization.com> or similar). Treatment type (PIO/PLA) will be coded to de-identify treatment (Example: treatment A and treatment B or similar) to blinded staff. Assigned unblinded staff, responsible for administering the treatment to volunteers, will be responsible for creating treatment codes to match treatment. They will maintain record of randomization scheme and treatment.

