Steady-State Treadmill Exercise: Results from a $\dot{\text{V}}\text{O}_{\text{peak}}$ assessment under HA conditions will be used to prescribe intensities for treadmill exercise on experimental trial days utilizing ACSM equations to estimate the speed and grade of the treadmill. Volunteers will complete 80-min of metabolically-matched, steady-state exercise at 55 \pm 5% of their $\dot{\text{V}}\text{O}_{\text{peak}}$ determined at HA. A practice session will be conducted during the baseline period to confirm prescribed speed and grade are appropriate to induce target $\dot{\text{V}}\text{O}_2$ and allow the research team to make modifications to prescribed speed and grade if needed to induce target $\dot{\text{V}}\text{O}_2$. The practice session will range ~40-80 minutes in length. The speed and grade determined during the practice session will be used to induce the same absolute intensity between study arms. The mode, duration, and intensity of steady-state exercise were chosen to mimic our past investigations (3, 4).

Carbohydrate Tracer Studies: After a 10 hr overnight fast, two catheters will be placed into the lower arm (one in each arm). One arm will be used for infusion of 6,6-[$^2\text{H}_2$] glucose tracer and the other will be used for blood sampling. Following an initial blood and breath sample collection to determine background enrichments, a primed, continuous infusion of 6,6-[$^2\text{H}_2$] glucose (Cambridge Isotope Laboratory, Andover, MA, USA) will begin (prime, 82.2 $\mu\text{mol}\cdot\text{kg}^{-1}$; continuous rate, 0.78 $\mu\text{mol}\cdot\text{kg}^{-1}\cdot\text{min}^{-1}$) (24, 25) for 2 hrs before and during exercise. Volunteers will complete 80-min of steady-state exercise on a treadmill, with $\dot{\text{V}}\text{O}_2$, $\dot{\text{V}}\text{CO}_2$, HR, and SaO_2 measured at approximately 5, 20, 40, 50, 60, and 75 min. During exercise volunteers will consume a glucose beverage at 1.8 g/min. Drinks will contain 145 g glucose, with a total volume of 1450 mL. The drink will be consumed in four boluses throughout the 80-min of steady-state exercise (0, 20, 40, and 60 min). The first bolus will be 550 mL, with the remaining three being 300 mL. The glucose beverage consumed during exercise will be enriched with 200 mg ^{13}C -glucose (Cambridge Isotope Laboratory) to increase the isotopic enrichment well above natural levels and optimize the measurement of exogenous glucose oxidation.

Figure 3: Carbohydrate Tracer Studies

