Blood Sampling (credentialed procedure): Blood samples will be collected using an indwelling catheter kept patent using IV saline at approximately at approximately -300, -120, -30, 0, 20, 40, 60, 80, and 140 min during exercise by a USARIEM credentialed phlebotomist. Baseline blood sampling will occur after a 10-hr overnight fast on experimental trial days. A total of 18 blood samples will be completed during this study taking ~340 mL of blood sampled from each volunteer over the experimental trial days (**Table 3**). Blood samples will be used for isotope analysis assessment, substrate and hormone responses, and iron markers (**Table 3**).

For glucose kinetic analysis, the tracer/tracee ratio (6,6-[²H]₂] glucose/glucose) using gas-chromatography-mass spectrometry (GCMS; Metabolic Solutions, Inc., Nashua, NH) (24), while ¹³C/¹²C in plasma glucose will be measured using isotope-ratio mass spectroscopy (IRMS; Metabolic Solutions).

Breath Sampling (non-credentialed procedure): Breath samples will be collected at approximately -300, 0, 20, 40, 45, 50, 55, 60, 65, 70, 75, and 80 min during exercise to determine exogenous glucose oxidation using single-patient breath collection bags (Quin-Tron Instrument Company, Milwaukee, WI, USA). Baseline breath sample will also be collected prior to correct for background of naturally occurring ¹³C. The natural enrichment of the glucose ingested and the ¹³C/¹²C in expired gas samples will be analyzed using isotope-ratio mass spectroscopy (Metabolic Solutions, Inc., Nashua, NH).

B5.4 Data Collection

Table 2. Outcome Variables

Data Element/Variable	Source	Operational Specification
Anthropometric data	Direct measurement	Height, weight, body composition
Substrate oxidation	Blood and breath	Glucose turnover, carbohydrate, fat, and protein oxidation
Metabolic response	Blood	Substrate analytes, hormones, inflammation, iron status

Table 3. Blood Analytes

Analyte	Time points (min)								
	-300	-120	-30	0	20	40	60	80	140 ⁴
Glucose ¹	x	x	x	x	x	x	x	x	x
Insulin ²	x			x	x	x	x	x	x
Free fatty acids ²	x			x	x	x	x	x	x
Lactate ²	x			x	x	x	x	x	x
Glycerol ²	x			x	x	x	x	x	x
Norepinephrine ²	x			x	x	x	x	x	x
Epinephrine ²	x			x	x	x	x	x	x
Hemoglobin ¹	x			x				x	
Hematocrit ¹	x			x				x	
¹³ C-glucose ³				x	x	x	x	x	x
6,6-[² H ₂] glucose ³		x	x	x	x	x	x	x	x
PBMC ¹	x			x				x	x
TNF α ¹	x			x				x	x
IL-6 ¹	x			x				x	x
IL-10 ¹	x			x				x	x
Hemooxygenase 1 ¹	x			x				x	x
Adiponectin ¹	x			x				x	x
Erythropoietin ¹	x			x					

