Hepcidin ¹	x			x					
Soluble transferrin receptor ¹	x			x					
Erythroferrone ¹	x			x					
Platelet derived growth factor-BB ¹	x			x					
Ferritin ¹	x			x					
Serum Iron ¹	x			x					
Transferrin Saturation ¹	x			x					
C-reactive protein ¹	x			x					
Archive	x	x	x	x	x	x	x	x	x

Samples will be analyzed at ¹USARIEM, ²Pennington Biomedical Research Center (Baton Rouge, LA), and ³Metabolic Solutions (Nashua, NH). ⁴Final blood draw at ~140 min will be taken under normoxic conditions in both trials. All blood samples will be separated into plasma and serum through centrifugation, aliquoted, and stored at -80°C until analysis or shipment. Study samples will be collected and aliquoted at USARIEM and specific samples will be shipped on dry ice to Pennington Biomedical Research Center, and Metabolic Solutions. Serum iron and transferrin saturation will be measured using an automated clinical chemistry

and immunoassay analyzer (Dimension: Siemens Healthcare Diagnostic, Deerfield, IL, USA). Serum soluble transferrin receptor, interleukin-6, hepcidin, platelet-derived growth factor-BB, erythropoietin, erythroferrone, and C-reactive protein will be determined using enzyme-linked immunosorbent assays. Blood sent out to other laboratories for analysis will not have any remaining samples after analysis is completed. USARIEM will retain all archive samples.

Plasma Glucose Turnover Calculations

For calculation of plasma glucose turnover the Steele equation with modifications for non-steady state will be used (26). Enrichment (E) will be expressed as mole percent excess (MPE); calculated as $(TTR)/(1 + TTR)$, where TTR is the tracer to tracee ratio. Appropriate corrections for skewed abundance distribution and overlapping spectra will be made for the TTR of the glucose tracers, 6,6-[²H₂] glucose and U-¹³C-glucose (26). From these calculations, total glucose Ra will be comprised of rates of appearance of exogenous (i.e., ingested) glucose and of endogenous (i.e., hepatic glucose production and negligible renal glucose production or splanchnic glucose) glucose (26):

$$\text{Total glucose } R_a \text{ (Total } R_a) = (F - ((pV \times ((C_2 + C_1)) / 2) \times ((E_2 - E_1) / (t_2 - t_1)))) / ((E_2 + E_1) / 2)$$
$$\text{Glucose } R_d = \text{Total } R_a - (pV (C_2 - C_1) / (t_2 - t_1))$$

$$\text{Exogenous glucose } R_a \text{ (Exo } R_a) = ((\text{Total } R_a + F) \times ((G_2 + GE_1) / 2) + (pV \times ((C_2 + C_1) / 2)) \times ((G_2 - G_1) / (t_2 - t_1)))$$

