$$\text{Endogenous glucose } R_a = \text{Total } R_a - \text{Exo } R_a$$

$$\text{Metabolic Clearance Rate (MCR)} = \text{Glucose } R_d / ((C_2 + C_1) / 2)$$

Where F represents the infusion rate of 6,6-[²H₂] glucose; pV is the effective volume of distribution for glucose, C₁ and C₂ are plasma glucose concentrations at t₁ and t₂, respectively, E₁ and E₂ are plasma enrichments of 6,6-[²H₂] glucose at t₁ and t₂, respectively, and E_d and E_p are tracer enrichments of U-¹³C-glucose from the test drink and plasma, respectively.

Calculations of Carbohydrate and Fat Oxidation

Carbohydrate and fat oxidation rates will be calculated from $\dot{V}O_2$ (L/min) and $\dot{V}CO_2$ (L/min) during the 80-min exercise bout as described by Jeukendrup and Wallis (27):

$$\text{Fat oxidation (g/min)} = (1.695 \times \dot{V}O_2) - (1.701 \times \dot{V}CO_2)$$

$$\text{Carbohydrate oxidation (g glucose/min)} = (4.585 \times \dot{V}CO_2) - (3.226 \times \dot{V}O_2)$$

Calculations of Exogenous and Endogenous Glucose Oxidation

Exogenous and plasma glucose oxidation will be calculated as (7):

$$\text{Exogenous glucose (g/min)} = \dot{V}CO_2 [(R_{exp} - R_{ref}) / (R_{exo} - R_{ref})] / k$$

$$\text{Plasma glucose (g/min)} = \dot{V}CO_2 [(R_{exp} - R_{ref}) / (R_{glu} - R_{ref})] / k$$

where $\dot{V}CO_2$ is in L/min, R_{exp} is the observed isotopic composition of expired CO₂, R_{ref} is the isotopic composition of expired CO₂ at rest before ingestion of the first dose of ¹³C-glucose, R_{exo} is the isotopic composition of the exogenous glucose ingested, R_{glu} is the isotopic composition of plasma glucose, and k (0.747 L/g) is the volume of CO₂ provided by the complete oxidation of glucose. Total endogenous glucose oxidation can be calculated by subtracting exogenous glucose oxidation from total CHO oxidation.

Endogenous glucose oxidation derived from muscle and liver can be determined by subtracting plasma glucose oxidation from total carbohydrate oxidation (muscle), and subtracting exogenous carbohydrate oxidation (liver) from plasma glucose oxidation (7). The first 40 min of steady-state exercise will allow for equilibration between the ¹³C/¹²C in expired CO₂ and the ¹³C/¹²C in CO₂ produced in tissues (28). Thus, endogenous glucose oxidation will only be calculated from samples obtained in the last 40 min of steady-state exercise (40 to 80 min).

Blood Analytes

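### With E defined as TTR/(1+TTR), the glucose appearance equations add a small excess of infused tracer to exogenous Ra and leave the rest in endogenous Ra; the symbol G is undefined

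*Combined protocol and SAP*

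**What the plan says.** B5.4, Plasma Glucose Turnover Calculations, states that "Enrichment (E) will be expressed as mole percent excess (MPE"), computed as TTR/(1+TTR). It then says that "total glucose Ra will be comprised of rates of appearance of exogenous (i.e., ingested) glucose and of endogenous" glucose, and prints (a bar marks the mean of the two time points):

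- Total Ra = (F − pV·C̄·ΔE/Δt) / Ē
- Rd = Total Ra − pV·ΔC/Δt
- Exo Ra = (Total Ra + F)·Ḡ + pV·C̄·ΔG/Δt, with one term of the mean printed as GE_1
- Endogenous Ra = Total Ra − Exo Ra
- MCR = Rd / C̄

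The legend defines F, pV, C and E, and adds that "E_d and E_p are tracer enrichments of" U-13C-glucose from the test drink and plasma. It does not define G, and neither E_d nor E_p enters a printed turnover equation.

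B5.3 (Carbohydrate Tracer Studies) gives the infusion as "continuous rate, 0.78" µmol/kg/min. For the drink it says: "The glucose beverage consumed during exercise will be enriched with 200 mg" of 13C-glucose, in 145 g of glucose. B5.3 (Research Procedures) also says: "Isotope methodology and aerobic exercise protocols will be identical to our previous work (3, 4), allowing comparison of outcomes across studies".

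**The concern.** Two things do not fit together.

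First, the exogenous equation cannot be evaluated from its own legend. G is used three times and never defined, while two symbols are defined and never used. G = E_p/E_d suits the printed layout, but the plan does not say so.

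Second, the section mixes two conventions. Adding F inside Exo Ra, and not subtracting it from endogenous Ra, is coherent if E is the tracer-to-tracee ratio. The text instead sets E to the mole fraction, under which F is already inside Total Ra.

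Glucose turnover is part of Objective 1 in B4. At stake are the split of glucose appearance into ingested and endogenous parts, and the comparability of that split with the earlier studies.

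**Working it through.** The plan states no Ra value, so there is no figure to reproduce. The check is a mass balance followed by numbers.

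**What Total Ra contains.** With E = tracer/(tracer + tracee), C total plasma glucose and Ra_all every inflow including the infusion:

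- tracer: d(pV·C·E)/dt = F − Rd·E
- all glucose: pV·dC/dt = Ra_all − Rd

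Expanding the first and substituting the second gives Ra_all = (F − pV·C·dE/dt)/E. This is the printed Total Ra, so Total Ra = exogenous + endogenous + F.

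**What Exo Ra should be.** With G the drink-derived fraction of plasma glucose, d(pV·C·G)/dt = Exo Ra − Rd·G. Hence Exo Ra = Ra_all·G + pV·C·dG/dt, and no further F is due. The printed form exceeds this by F·G. Endogenous Ra should be Total Ra − F − Exo Ra; the printed form exceeds this by F − F·G = F·(1−G).

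**Steady-state example.** F = 0.78 (B5.3). Assumed: unlabelled Ra 30 µmol/kg/min, 30% from the drink, so true exogenous 9 and endogenous 21.

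- Total Ra = 30 + 0.78 = 30.78; G = 9/30.78 = 0.2924
- Printed Exo Ra = (30.78 + 0.78) × 0.2924 = 9.228, an excess of 0.228 = F·G (2.5%)
- Printed endogenous = 30.78 − 9.228 = 21.552, an excess of 0.552 = F·(1−G) (2.6%)
- Corrected: 30.78 × 0.2924 = 9.000, and 30.78 − 0.78 − 9.000 = 21.000
- Extra F dropped but not subtracted: endogenous = 30.78 − 9.000 = 21.78 (3.7% too high)
- E as TTR with the printed equations: Total 30.00, exogenous 9.000, endogenous 21.000

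**Non-steady state.** One-pool simulation, interval 40–60 min. Assumptions: C is 5 mmol/L, rising 1 mmol/L over 80 min; exogenous Ra rises to a plateau with a 15-min time constant; endogenous/plateau exogenous 20/15, 10/15, 30/10, 20/5 and 15/20 µmol/kg/min; pV 0.10, 0.16 and 0.23 L/kg. That makes 15 scenarios.

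| Form | Exo Ra error | Endogenous Ra error |
|---|---|---|
| As printed | −0.4% to +1.1% | about +2.0% to +5.5% |
| Extra F dropped only | −2.3% to −0.5% | +2.6% to +7.8% |
| Extra F dropped, F subtracted | −2.3% to −0.5% | 0.0% |

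For 20/15 with pV 0.16, truth is 14.42 and 20.00. Total Ra is 34.99; the printed form gives 14.45 and 20.54, the corrected form 14.21 and 20.00. The gap between the two exogenous values is the extra F; over all scenarios it raises Exo Ra by 1.3–2.5%. With the interval shrunk to 0.01 min the corrected form is exact, while the printed form is +1.5% to +2.7% (exogenous) and +2.0% to +5.1% (endogenous). If endogenous Ra falls during exercise, the printed endogenous error is +2.5% to +5.7% and the corrected error −0.3% to +0.1%.

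**Between arms.** In four assumed placebo-versus-pioglitazone pairs at three pV values, the printed contrasts differ from truth by at most 0.05 (exogenous) and 0.09 (endogenous) µmol/kg/min, for true differences of about 0–5.

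**The case against.** The best defence is that little depends on this. Rd and MCR are built from Total Ra, and Rd is right with E as a mole fraction, because the infused tracer is also cleared. Exogenous oxidation comes from breath. B5.8.2 names no test of exogenous or endogenous Ra. All of this stands, and it is why the point is minor.

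A second objection is that the correction does not bring exogenous Ra closer to truth over every sampling interval. At 40–60 min the printed form is closer in 12 of 15 scenarios, and at 20–40 min in 14 of 15; the corrected form is closer in 14 of 15 at 60–80 min and in all at 0–20 min. This stands as a fact, but the printed form gains only because its extra F happens to offset trapezoid error. The drink is also given in boluses. With an assumed bolus input at 20–40 min, Exo Ra error reached −4.5% as printed and −6.3% corrected, so 20-min sampling can matter more than the extra F.

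Third, GE_1 may be a PDF reading artefact, and a divisor may have been lost. That should be checked on the source page. It does not explain a complete legend sentence that omits G.

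A reader might infer that the whole of F is counted twice and the whole of F left in endogenous Ra. The algebra gives only F·G and F·(1−G). A reader might also infer that exogenous Ra will be wrong several hundredfold, since reading G as raw plasma enrichment would shrink it by roughly 145 g/0.2 g = 725. The plan does not say that G is raw enrichment, and such values would be noticed at once.

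**Conclusion.** Wrong as written, and minor. That Total Ra includes F follows from the plan's own definition of E by algebra alone, and the undefined G is plain on the page. The sizes rest on assumed fluxes (endogenous 10–30, exogenous plateau 5–20 µmol/kg/min), a one-pool model with smooth drink input, and G = E_p/E_d: endogenous Ra about 2–5.5% too high at 40–60 min, and exogenous Ra raised by about 1.3–2.5% by the extra F.

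It would be tempting to conclude that Hypothesis 1 or the sample size is compromised. The documents do not support that: exogenous glucose oxidation, Rd, MCR, Table 4 and the tests in B5.8.2 do not use Exo Ra. F per kg is the same in both arms, so the between-arm effect is negligible. Nor do the documents show that the calculations actually used contain the error; they show only that the text cannot be followed as printed.

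**What to change.** In B5.4:

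- Define G = E_p/E_d and correct GE_1.
- Say how the measured 13C/12C ratios of plasma glucose and drink become E_p and E_d. B5.3 (Breath Sampling) mentions only "The natural enrichment of the glucose ingested and the" breath ratio, whereas E_d needs the enrichment of the spiked drink. The breath equation already needs that measurement, since its R_exo "is the isotopic composition of the exogenous glucose ingested".
- Keep E = TTR/(1+TTR) and state that Total Ra includes F.
- Set Exo Ra = Total Ra·Ḡ + pV·C̄·ΔG/Δt.
- Set Endogenous Ra = Total Ra − F − Exo Ra. Do not drop the extra F without this second change.

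This leaves Rd and MCR unchanged. Switching E to TTR would also be coherent with C as tracee glucose, but it would move Rd and MCR, both Hypothesis 1 outcomes, by about 2–4%, and it is not needed.

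The cost is equation and legend text and a check that the calculation sheet agrees; no new blood samples. There are two downsides. Over 20-min intervals the corrected Exo Ra can lie further from truth than the printed form. And if the earlier studies used the printed form, both forms should be reported, or the earlier values recomputed, so that the promised cross-study comparison holds.
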